9.5 Other Clinical Events

Management of sexually transmitted infections commonly referred to as STIs and other forms of vaginitis, cervicitis, urethritis will be in accordance with current CDC guidelines (<http://www.cdc.gov/std/treatment/>). When clinically appropriate, investigators should use oral or parenteral (in the case of syphilis, for example) medications when at all possible to avoid intravaginal medication use. Incident STIs necessitate termination from study.

If any participant has a symptomatic UTI the participant will be referred for treatment and the visit will be rescheduled after treatment is complete and symptoms have resolved. Further details regarding management of Other Clinical Events will be provided in the SSP (www.mtnstopshiv.org/).

9.6 HIV-1 Infection

If a male or female participant has a positive test for HIV-1, study product must be held for the female participant. See Section 9.3 for additional details.

9.7 Pregnancy

Pregnancy testing will be performed at scheduled study visits and participants will be encouraged to report all signs or symptoms of pregnancy to study staff. The IoR/designee will counsel any participant who becomes pregnant regarding possible risks to the fetus according to site SOPs. The IoR/designee also will refer the participant to all applicable services; however, sites will not be responsible for paying for pregnancy-related care.

A participant who is pregnant at study termination will continue to be followed until the pregnancy outcome is ascertained (or, in consultation with the PSRT, it is determined that the pregnancy outcome cannot be ascertained). Pregnancy outcomes will be reported on relevant CRFs; outcomes meeting criteria for EAE reporting also will be reported on EAE forms.

A participant who becomes pregnant during the course of study participation may be offered participation in MTN-016, HIV Prevention Agent Pregnancy Exposure Registry: EMBRACE Study, at sites participating in MTN-016. This registry study captures pregnancy outcomes as well as infant health information, (including growth and development), to evaluate the safety and teratogenic risks of microbicide and oral PrEP exposure in pregnancy.

Participants who become pregnant during the course of the study will permanently discontinue study product use and, along with their participating partner, will be terminated from the study.

9.8 Criteria for Early Termination of Study Participation

Participants may voluntarily withdraw from the study for any reason at any time. The IoR/designee also may withdraw participants from the study to protect their safety and/or if they are unwilling or unable to comply with required study procedures, after consultation with the PSRT. Participants also may be withdrawn if the study sponsors, government or regulatory authorities, including the MTN, CONRAD, NIAID, FDA and Office for Human Research Protections (OHRP), or site IRBs terminate the study prior to its planned end date. Every reasonable effort is made to complete a final evaluation

of participants who withdraw or are withdrawn from the study prior to completing follow-up. Study staff members will record the reason(s) for all withdrawals in participants' study records.

10 STATISTICAL CONSIDERATIONS

10.1 Overview and Summary of Design

This is a Phase 1, multi-site, non-randomized, multi-sequence, open-label study. The trial will enroll participants into Single Dose/BAT Cohort (Group 1) and into the Multiple Dose Cohort (Group 2). Couples in Group 1 will be followed for approximately 8 weeks (2 menstrual cycle). Couples in Group 2 will be followed for approximately 14 weeks (3 menstrual cycles).

Group 1

Women in Group 1 will apply a single dose of gel 1 hour prior to coitus at Visit 3a (Gel -1/Coitus). Sampling should occur no more than 2 hours after the coital episode (Visit 3b (Post-Coital Sampling)). After a 10-day washout period (minimum), women will apply a single dose of gel at Visit 4a (Gel -1/No Coitus) without engaging in coitus and have samples collected at Visit 4b (Sampling) at approximately the same time post-gel application as at Visit 3b (Post-Coital Sampling). Women in Group 1 will then apply a single dose of gel 24 hours prior to coitus at Visit 5a (Gel -24/Coitus) and have samples collected at Visit 5b (Post-Coital Sampling). After a minimum 10-day washout period participants will apply a single dose of gel at Visit 6a (Gel -24/No Coitus) without engaging in coitus and have samples collected at Visit 6b (Sampling) at approximately the same time post-gel application as at Visit 5b (Post-Coital Sampling). Finally, women in Group 1, after a final 10-day washout period, will apply a single dose of gel at Visit 7a (Gel -1/Coitus/Gel +1) approximately 1 hour prior to coitus and then engage in sex and apply a second dose of study product approximately 1 hour after coitus. Samples will be collected no more than 2 hours after the coital episode at Visit 7b/Final (Post-Coital Sampling).

Group 2

Women in Group 2 will apply a single dose of gel for seven consecutive days starting at Visit 2 (Enrollment- Provision of Study Product) with the 7th dose applied again 1 hour prior to coitus at Visit 3a (Gel -1/Coitus) and have samples collected at Visit 3b (Sampling). After a minimum 20 day washout period, female participants will receive a provision of study product and will dose for seven consecutive days Visit 4 (Provision of Study Product) with the last dose administered at Visit 5 (Sampling) and samples collected at approximately the same time post-gel application as at Visit 3b (Sampling). Following another minimum 20 day washout period, female participants will apply a single dose of gel for seven consecutive days, starting at Visit 6 (Provision of Study Product) with the 7th dose applied approximately 72 hours before the coital episode at Visit 7a (Gel -72/Coitus). Sampling should occur no more than 2 hours after the coital episode at Visit 7b (Post-Coital Sampling). Another 20 day minimum washout period will occur and female participants will return to the clinic to receive a provision of study product at Visit 8 (Provision of Study Product). Participants will dose for seven consecutive days with the last dose administered 72 hours prior to Visit 9/Final (Sampling) and samples will be collected at approximately the same time post-gel application as at Visit 7b (Post-Coital Sampling).

Participants will be monitored for various adverse events, including all genital, genitourinary, and reproductive system AEs, as specified in Section 8 Assessment of Safety. Clinical management and study product discontinuation guidelines are detailed in Section 9 Clinical Management.

10.2 Study Endpoints

10.2.1 Primary Endpoints

Consistent with the primary study objective to assess the impact of coitus (and semen) on the pharmacokinetics (PK) of tenofovir 1% gel in female genital tract secretions, vaginal and cervical tissue and rectal tract secretions, the following primary endpoints will be assessed:

- **PK.** Tenofovir and tenofovir diphosphate levels (from cellular samples) from cervicovaginal lavage (CVL), cervical cytobrush, tissue biopsies (vaginal and cervical), blood, and rectal sponge following tenofovir 1% gel use in the absence of or following coitus.

Consistent with the primary study objective to assess the impact of coitus (and semen) on pharmacodynamics (PD) of luminal drug by measuring the anti-HIV-1 activity in CVL samples, the following primary endpoint will be assessed:

- **PD.** Anti-HIV-1 activity in CVL

10.2.2 Secondary Endpoints

Consistent with the secondary study objective to assess the acceptability of the MTN - 011 trial to male and female participants, the following secondary endpoints will be assessed:

- **Acceptability.** Overall experience with participating in the clinical trial and willingness to participate in a future trial.

10.2.3 Exploratory Endpoints

Consistent with the exploratory objective:

- To determine impact of coitus and/or tenofovir on the genital tract mucosal environment

The following exploratory endpoint will be assessed:

- Measurement of biomarkers of mucosal immunity

Consistent with the exploratory objective:

- To determine whether a semen biomarker can be used to estimate the volume of ejaculate within CVL

The following exploratory endpoint will be assessed:

- Measurement of semen biomarker in ejaculate and in CVL

Consistent with the exploratory objective:

- To assess whether sufficient drug is retained in the lumen in the absence of or following coitus to inhibit HSV-2 as an additional surrogate biomarker of pharmacodynamics

The following exploratory endpoint will be assessed:

- Anti-HSV-2 activity in CVL

10.3 Primary Study Hypothesis

The study hypotheses for the primary objective are:

- Coitus will not impact the pharmacokinetics of TFV following a single precoital dose, BAT or multiple applications of study product

- Coitus will not alter the antiviral activity in genital tract secretions following single pre-coital dose, BAT or multiple applications of study product

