The results of this comparison can only be fully understood if both variables (sex and gel) are controlled for. Thus, controls will include dosing and sampling in the absence of sex (both Groups) or in the absence of gel (Group 1 only). In all cases, clinical samples will be obtained ~2 hours after sex or a matched timepoint (no sex). Mucosal secretions have “endogenous” antiviral activity, which likely reflects the cumulative effects of antimicrobial peptides, pH, and other mucosal mediators. The physical act of intercourse may alter this activity, reflecting contributions from semen and/or its impact on the female genital tract. Thus, CVL obtained at the Screening visit (no gel/no sex) and the Enrollment Visit, where no gel will be applied, but sex will occur,) for Group 1 participants will provide baseline data in the absence of any gel product (See Section 7 for additional details). If tenofovir retains its antiviral activity following sex, then the anti-HIV activity in the CVL sample collected at the Gel/Sex Visit should be comparable to that of a sample collected at the Gel/No Sex Visit and should be greater than that of the sample collected at the visits without gel dosing (No Gel/No Sex, No Gel/Sex visits).

This unique design allows each participant to serve as their own control for these comparisons.

We hypothesize that coitus and semen may not have the same impact on PK/PD in the setting of daily gel application due to continual accumulation of drug in cervicovaginal tissue over time. Thus Group 2 will compare PK/PD after 7 daily doses of gel in the absence of sex to that of the PK/PD after the couple engages in sex. While the 7-day dosing regimen is insufficient to establish steady-state tenofovir diphosphate concentrations for all women in cells and tissue (intracellular median half-life [interquartile range] 61 (49-112 hours in peripheral blood mononuclear cells [PBMC], possibly shorter in tissue)⁶, the concentrations in tissue and cells achieved will enable us to test the study hypotheses. Furthermore, longer dosing periods may yield less reliable data as participant adherence to study product use may vary over time.

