2.5 Clinical Studies

2.5.1 Clinical Studies of Tenofovir

Pharmacokinetics

A Phase 1 Safety and Acceptability Study of the Vaginal Microbicide Agent PMPA Gel, also known as HPTN 050, a study of tenofovir vaginal gel with published data, examined the PK of tenofovir gel.¹⁶ Eighty-four (60 HIV negative and 24 HIV positive) women applied either 0.3% or tenofovir 1% gel once or twice daily for 14 days. Systemic absorption was limited (maximum serum levels 3.1-25.8 ng/mL).

A randomized trial to assess anti-HIV activity and soluble mucosal immunity following application of tenofovir gel also provided data on the PK of tenofovir gel.¹⁷ With daily dosing, 12 participants in the tenofovir arm of the study yielded mean (SD) CVL tenofovir levels at Days 3, 7, and 14 of 9.5×10^3 (11.2×10^3), 24.7×10^3 (26.4×10^3), and 16.0×10^3 (20.5×10^3) ng/mL, respectively.

A study of the pharmacokinetics of tenofovir gel was conducted among 49 sexually abstinent women in the USA and Dominican Republic (CONRAD A04-095, IND 73,382).¹⁸ The following are results from a subset (n=21) who completed the single-dose phase. Following an intravaginal dose (4 g) of tenofovir gel, blood samples were obtained at 0.5, 1, 2, 4, 6, 8, and 24 hr(s) from all participants. Participants were randomized to one of seven time-points [0.5, 1, 2, 4, 6, 8, and 24 hr(s)] for vaginal fluid collection and vaginal biopsies. Total tenofovir (TFV) was measured in blood plasma, fluid, and biopsies. Most blood plasma TFV concentrations were below 5 ng/mL. Four had higher values (up to 19.5 ng/mL), which were not sustained. Vaginal fluid concentrations were high, generally $1.5\text{-}5.0 \times 10^6$ ng/mL through 8 hrs and $4.5\text{-}47.1 \times 10^4$ ng/mL at 24 hrs. The mean concentration in vaginal tissue at 0.5, 1, 2, 4, 6, 8 and 24 hr(s) were 275×10^3 , 450×10^3 , 186×10^3 , 89×10^3 , 69×10^3 , 24×10^3 and 15×10^3 ng/g of tissue, respectively, (LLOQ=1 ng/mL) with a peak at 1-4 hrs. Vaginal fluid elimination appeared linear. Tissue elimination appeared to follow a multi-compartment model. Total TFV was detectable in vaginal tissue and fluid up to 24 hrs post single-dose exposure.

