After a minimum 10-day washout period, couples will return to the clinic for Visit 5a (Gel -24hr/Coitus), females participants insert a single dose of gel vaginally 24 hours prior to engaging in coitus. Participants will receive coital visit instructions which will include information regarding the timing of study product application (24 hours prior to sex), when participants should return to the study clinic (no more than 2 hours after completing the coital act), and other information to ensure participants comply with study requirements. Sampling procedures will occur approximately 2 hours after coitus at Visit 5b (Post-Coital Sampling).

Following a 10-day minimum washout period, the female participant will return to the clinic for Visit 6a (Gel -24/No Coitus). She will apply one applicator of tenofovir 1% gel in the clinic and will return to the clinic approximately 24 hours later for Visit 6b-Sampling.

Following a minimum 10-day washout period, couples will return for Visit 7a/b (Gel -1/Coitus/ Gel +1), females will insert into the vagina the content of one applicator of tenofovir 1% gel approximately 1 hour prior to engaging in coitus and approximately 1 hour after coitus. Both doses of the study product will be vaginally inserted at the location where coitus is to occur (hotel or comparable site). Sampling procedures will occur approximately 2 hours after coitus at Visit 7b (Post-Coital Sampling/ Final Clinic). Male partners will be asked to attend Visit 7b (Post-Coital Sampling/ Final Clinic) as well. Study visit instructions will be provided to participants.

Table 7: Group 1- Visit 2a: Enrollment No Gel/Coitus, Visit 3a: Gel -1/Coitus, Visit 4a: Gel-1 /No Coitus, Visit 5a: Gel -24/Coitus, Visit 6a: Gel -24/No Coitus, Visit 7a: Gel -1/Coitus/ Gel +1

Group 1 Visit 2a: Enrollment No Gel/Coitus, Visit 3a: Gel -1/Coitus, Visit 4a: Gel-1 /No Coitus, Visit 5a: Gel -24/Coitus, Visit 6a: Gel -24/No Coitus, Visit 7a: Gel -1/Coitus/ Gel +1			
Component	Female Participants	Male Participants	

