The difference in drug concentration levels at the visits where the female participants dose with gel and engage in coitus vs. the visits where female participants dose with gel and do not engage in coitus will be analyzed using the paired t-test or Wilcoxon signed-ranks test, as appropriate. In Group 1, for assessment of the BAT dosing regimen, DC from the visit where female participants perform BAT dosing with gel, coitus, and post-coitus gel will be compared to DC from the visit where female participants dose with gel (-1 hour) and do not engage in coitus. The BAT DC will also be compared to the visit where female participants dose with gel (-1 hour) and engage in coitus.

For each of the nine (9) assessments, the estimate of the mean percentage change along with the corresponding two-sided p-value and a 95% confidence interval will be presented. Significance level p-values will be adjusted for multiple comparisons using the FDR method.

In addition, change in amount (mass) of vaginal drug after dosing will also be assessed in CVL in similar fashion. As an explanatory variable, the screening semen sample from the male partner will be used to assess the typical semen biomarker value for each male participant so that the volume of ejaculate can be assessed using the CVL.

Primary Pharmacodynamic Analysis

In order to assess the impact of coitus (and semen) on pharmacodynamics (PD) of luminal drug by measuring the anti-HIV-1 activity in CVL samples, antiviral activity (percent inhibition) will be compared at various visits within each cohort. For Group 1, the difference in mean percent inhibition will be compared between:

1. No gel use with coitus vs. endogenous activity (baseline) (impact of coitus on endogenous activity)

For each group, and dose timing (-1 and -24 hours in Group 1 and -1 and -72 hours in Group 2), the difference in mean percent inhibition will be compared between:

2. Gel use alone vs. endogenous activity (baseline) (PD in absence of coitus)
3. Gel use with coitus vs. endogenous activity (baseline) (PD of product following coitus compared to baseline CVL activity)
4. Gel use alone vs. gel use with coitus (Difference in PD in the absence vs following coitus)
5. Gel use with coitus vs. no gel use with coitus (Group 1 only) (PD of product following coitus compared to post-coitus endogenous activity)

In Group 1, for assessment of the BAT dosing regimen, the difference in mean percent inhibition will be compared between:

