1. Gel use, coitus, and post-coital gel use vs. endogenous activity (baseline) (PD of BAT compared to baseline CVL activity)
2. Gel use, coitus, and post-coital gel use vs. gel use (-1 hour) alone (Difference in PD of BAT compared to absence of coitus and post-coital gel)
3. Gel use, coitus, and post-coital gel use vs. gel use (-1 hour) with coitus (Difference in PD of BAT compared to absence of post-coital gel)
4. Gel use, coitus, and post-coital gel use vs. no gel use with coitus (PD of BAT compared to post-coitus endogenous activity)

Differences will be assessed with the use of the paired t-test or Wilcoxon signed-ranks test, as appropriate.

Secondary Acceptability Analysis

Descriptive statistics will be used to summarize behavioral, adherence, and acceptability data. Behavioral characteristics will be described in terms of the proportion of couples reporting sexual behaviors and practices prohibited during study participation. The adherence to product use will be described among couples in the Multiple Dose Cohort (Group 2) only, and will include assessment of the number and percentage of expected daily doses taken. The perceived acceptability of study procedures and use of the product will be described by the proportion of couples indicating that the product or procedures were found to be acceptable. The proportion of couples willing to take part in a trial of similar design in the future will be calculated. No formal testing will be performed.

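### The primary hypotheses claim a test of coitus under BAT dosing, but no BAT visit without coitus exists, so no planned contrast isolates that effect

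*Protocol*

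**What the plan says.** Section 10.3 gives the PK hypothesis as "Coitus will not impact the pharmacokinetics of TFV following a single precoital dose, BAT or multiple applications of study product", and a parallel hypothesis covers antiviral activity. Section 2.6.1 carries the same pair. Section 10.4.1 describes the primary PK endpoint as the effect of coitus after a single dose and BAT regimen in Group 1, and sizes the trial on a 25% change due to coitus.

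At Visit 7a gel is inserted "approximately 1 hour prior to engaging in coitus and approximately 1 hour after coitus" (section 7.3). On sampling, section 7.3 says "Sampling procedures will occur approximately 2 hours after coitus at Visit 7b (Post-Coital Sampling/ Final Clinic", and section 10.1 says "Samples will be collected no more than 2 hours after the coital episode at Visit 7b/Final (Post-Coital Sampling". Tables 1, 3 and 5 and Appendix I list no BAT visit without coitus.

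For PK, section 10.6.2 says that concentrations from the visit where women "perform BAT dosing with gel, coitus, and post-coitus gel will be compared to DC from the visit where female participants dose with gel" at -1 hour without coitus; BAT is also compared with Gel -1/Coitus. The PD list in the same section has the matching contrasts, plus BAT against baseline and against No Gel/Coitus. It describes the first as "Difference in PD of BAT compared to absence of coitus and post-coital gel".

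Section 2.1 sets the principle for the design: "The results of this comparison can only be fully understood if both variables (sex and gel) are controlled for".

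**The concern.** Every other gel-with-coitus condition has a no-coitus partner at the same dose and timing: Visits 3 and 4 and Visits 5 and 6 in Group 1, and Visits 3 and 5 and Visits 7 and 9 in Group 2. BAT has none, yet it sits in the same primary hypotheses. The nearest no-coitus visit has a different number of doses and a different time since the last dose, so a result from that contrast could be reported as an effect of coitus, or as no effect, when it is neither. The regimen matters: section 2.1 describes BAT as the dosing used most by women in CAPRISA 004, and helping to explain that trial is a stated purpose. An analysis plan cannot supply a control condition that is never observed.

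**Working it through.** **1. The plan's own power figure.** Section 10.4.1 assumes a 25% change, SD 37.5% and N = 20. For a paired t-test with two-sided alpha 0.05, df = 19 and noncentrality (0.25/0.375) × √20 = 2.98. Power is 0.807, which matches Table 18 and the stated 80%. The calculation is sound for a contrast in which only coitus differs.

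**2. What differs between the visits** (sections 6.2.1, 7.3 and 10.1)

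| Visit | Coitus | Doses | First dose to sample | Last dose to sample |
|---|---|---|---|---|
| 4b, Gel -1/No Coitus (A) | no | 1 | 1 + 2 = about 3 h | about 3 h |
| 3b, Gel -1/Coitus (B) | yes | 1 | 1 + 2 = about 3 h | about 3 h |
| 7b, BAT (C) | yes | 2 | 1 + 2 = about 3 h | 2 − 1 = about 1 h |
| BAT/No Coitus (D) | no | 2 | not observed | not observed |

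**3. Identification.** The hypothesis concerns C − D. Write C − D = (C − A) − (D − A). The term D − A, the second dose's contribution without coitus, is never observed. It can be replaced by C − B, the second dose's contribution with coitus, only if coitus does not alter that contribution. Then C − D = (C − A) − (C − B) = B − A, which is the single-dose coital effect. So the BAT visit adds information about coitus only where the needed assumption fails. The PD contrasts against baseline and No Gel/Coitus do not help, because neither comparator is BAT without coitus.

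**4. Size of the confounding if coitus has no effect**
- Mass applied, before clearance or leakage: 2/1 = 2.
- Tissue illustration. Section 2.5.1 ("The mean concentration in vaginal tissue at 0.5, 1, 2, 4, 6, 8 and 24 hr(s) were") gives 450, 186 and 89 × 10³ ng/g at 1, 2 and 4 h. At 3 h, log interpolation gives √(186 × 89) = 128.7, and linear interpolation gives (186 + 89)/2 = 137.5. With additive doses the ratio is (450 + 128.7)/128.7 = 4.5, or (450 + 137.5)/137.5 = 4.3.
- In the protocol's formula, (1 − ratio) × 100%, these are −100% for mass and about −350% or −327% for tissue.
- Sampling 1.5 to 2.5 h after coitus moves the tissue ratio between 2.7 and 4.5.

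**5. Adding a coital loss** (tissue illustration, log interpolation)

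| Loss | On dose 1 only | On both doses |
|---|---|---|
| 0% | 4.5 | 4.5 |
| 68% (mean in the PRO 2000 study, section 10.4.1) | (0.32 × 128.7 + 450)/128.7 = 3.8 | 0.32 × 4.5 = 1.44 |
| about 78% | not computed | 1 − 1/4.5 = 0.778, so ratio 1 |
| 90% | not computed | 0.10 × 4.5 = 0.45 |
| 100% | 450/128.7 = 3.5 | 0 |

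On mass alone with loss on both doses, the ratio is 2 × (1 − loss): 1.0 at 50% and 0.64 at 68%. The point of no difference therefore depends on the matrix and on which dose is lost.

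**6. Consequence for the test.** If the plan's SD applied here, a 25% shift caused by the second dose alone would be significant with probability 0.81.

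**The case against.** A reader might infer more than this: that the BAT result would suggest no coital loss whatever coitus does. The documents do not support that. It requires coitus to act on the first dose only. The second dose goes in about 1 h after coitus and could also be diluted or leak, and with losses on both doses the ratio falls to 1 and then below it.

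Nor would the planned test support the stated hypothesis on these figures. The hypothesis is no impact and the p-values are two-sided, so a large increase would reject it. False reassurance arises only if someone reads the increase as absence of coital loss.

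The tissue ratios are also weak evidence. They rest on 21 women over seven time points (21/7 = 3 each), one matrix, an interpolated 3 h value and assumed additivity. Section 2.5.1 reports vaginal fluid as generally 1.5 to 5.0 × 10⁶ ng/mL through 8 h, so time since last dose may matter much less in luminal fluid. They say nothing direct about tenofovir diphosphate, blood, rectal samples or percent inhibition.

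Finally, section 10.6.2 treats BAT in separate sentences, its PD list already names both differing factors, and the contrast has a fair descriptive use: how BAT levels compare with those seen without sex. Whether BAT enters the percentage-change family is unclear rather than stated.

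All of this limits the consequence. None of it supplies the missing comparator or reconciles the hypotheses with the visit schedule.

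**Conclusion.** The point holds as a mismatch between hypothesis and design. Sections 2.6.1, 10.3 and 10.4.1 claim to assess coitus under BAT, and no listed contrast identifies that effect without assuming that coitus leaves the second dose's contribution unchanged. This conclusion rests on the visit schedule alone.

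The size of the confounding is a ratio of 2 on mass applied and roughly 4.3 to 4.5 on the tissue illustration, both with no coital effect. The second range gives direction and scale only. A substantial coital loss could be masked, cancelled or reversed in sign, so this contrast supports no statement about coitus in either direction. The matched -1 h, -24 h and Group 2 contrasts are unaffected.

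**What to change.** - **Sections 2.6.1 and 10.3:** remove BAT from both coitus-impact hypotheses.
- **Section 10.4.1:** remove BAT from the impact-of-coitus power statement; the 25% and 37.5% inputs do not describe a BAT contrast.
- **Section 10.6.2, PK:** state that the BAT contrasts are outside the analysis of percentage change due to coitus. Label BAT vs Gel -1/Coitus as the effect of adding the post-coital dose. Label BAT vs Gel -1/No Coitus as a regimen comparison with no coital interpretation, naming both differing factors as the PD list does.
- **Section 10.6.2, PD:** keep the contrasts, including BAT vs baseline and vs No Gel/Coitus.

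The cost is wording only, with no added visits, samples or couples. The trial gives up a claim that its design cannot support.
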